^e If participants are not eligible to receive their 2nd dose, they immediately enter the follow-up period.

^f AEs will only be collected for 4 weeks following each study drug administration.

^g An aliquot of serum collected at baseline will be stored for testing (e.g. Platelet Factor 4 [PF4] antibody ELISA) should an AESI related to blood clots be reported anytime during the study period.

Follow-Up Period							
		COHORT 1	COF	IORT 2	COHORT 3		
Study Day	Months 3, 4, Month 7 5, 6 (Wk 28)/ EOS		Months 4, 5, 6, 7	Month 8 (Wk 32)/EOS	Months 5, 6, 7, 8	Month 9 (Wk 36)/ EOS	
Telephone Visit	Х		Х		Х		
Visit Window (days)	±7	±7	±7	±7	±7	±7	
Query for SAEs, AESIs and NOCIs	Х	Х	Х	Х	Х	Х	
Sample Collection Immunoger	nicity Assessme	nts					
Serum		Х		Х		Х	
Whole blood (Flow Based)							
Whole blood (PBMC) ^a		Х		Х		Х	
Nasal Swab (Sam Device)		Х		Х		Х	
Saliva		Х		Х		Х	

AE, adverse event; AESI, Adverse event of special interest; EOS, End of Study; ET, Early Termination; HCV, Hepatitis C Virus; HIV, Human Immunodeficiency Virus; NP, Nasopharyngeal; NOCI, New Onset of Chronic Illness; PBMC, peripheral blood mononuclear cells; SAE, serious adverse event. ^a Optional.

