4. OVERALL STUDY DESIGN

This is an open-label, boost-optimization study of an adenoviral- vector based oral norovirus vaccine (VXA-G1.1-NN) expressing GI.1 VP1 administered orally to health adult participants 18-55, inclusive. This study will enroll approximately 30 participants in three cohorts stratified by varying boost vaccination schedules.

The study will include a Screening period, Active study period through 4 weeks post last vaccination dose (Week 8 for Cohort 1, Week 12 for Cohort 2 and Week 16 for Cohort 3), and a Follow-up period of 6 months post vaccination (Month 7 for Cohort 1, Month 8 for Cohort 2 and Month 9 for Cohort 3). Study assessments will be conducted as shown in the SoA in Section 1.2 (Table 2). In addition, participants will be contacted monthly by phone between site visits to monitor for safety as specified in the SoA.

After signing an informed consent, participants will undergo screening assessments to determine study eligibility over a 45-day screening period.

On Day 1, participants will be enrolled sequentially in order of eligibility. Participants may be assigned to cohorts based on their availability for the second dose (boost). Cohorts 3 and 2 may be enrolled prior to Cohort 1 to optimize the overall study timeline.

Group	Study Drug	Dose (IU ±0.5 log)	Doses	Dosing Schedule	Subjects
Cohort 1	VXA-G1.1-NN	1x10 ¹⁰	2	Day 1 & Week 4	10
Cohort 2	VXA-G1.1-NN	$1 x 10^{10}$	2	Day 1 & Week 8	10
Cohort 3	VXA-G1.1-NN	$1 x 10^{10}$	2	Day 1 & Week 12	10
				Total	30

Eligible participants will be enrolled to receive their first dose of study vaccine on Day 1.

During the Active period, participants will record symptoms of reactogenicity daily for 1 week post each vaccination, administered based on Cohort assignment, using a Solicited Symptom Diary. Participants will return to the site as specified in the SoA to have safety assessments and samples collected for evaluation of immunogenicity.

Additionally, female participants of childbearing potential must have a negative pregnancy test before their second dose of study drug. Participants deemed unsuitable for the second dose due to acute illness or new medical condition may be re-assessed, and if the condition resolves, may have a delayed second dose administered within 1 week of their originally scheduled second-dose visit (+7 days window). Participants with a delayed second study drug administration will follow the delayed schedule through their active period.

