10. SUPPORTING DOCUMENTATION AND OPERATIONAL CONSIDERATIONS

10.1. Appendix 1: Regulatory, Ethical, and Study Oversight Considerations

10.1.1. Regulatory and Ethical Considerations

• This study will be conducted in accordance with the protocol and with the following:

Consensus ethical principles derived from international guidelines including the Declaration of Helsinki and Council for International Organizations of Medical Sciences (CIOMS) International Ethical Guidelines

Applicable ICH Good Clinical Practice (GCP) Guidelines

Applicable laws and regulations

- The protocol, protocol amendments, ICF, Investigator Brochure, and other relevant documents (e.g., advertisements) must be submitted to an IRB/IEC by the investigator and reviewed and approved by the IRB/IEC before the study is initiated.
- Any amendments to the protocol will require IRB/IEC approval before implementation of changes made to the study design, except for changes necessary to eliminate an immediate hazard to study participants.
- Protocols and any substantial amendments to the protocol will require health authority approval prior to initiation except for changes necessary to eliminate an immediate hazard to study participants.
- The investigator will be responsible for the following:

Providing written summaries of the status of the study to the IRB/IEC annually or more frequently in accordance with the requirements, policies, and procedures established by the IRB/IEC.

Notifying the IRB/IEC of SAEs or other significant safety findings as required by IRB/IEC procedures.

Providing oversight of the conduct of the study at the site and adherence to requirements of 21 CFR, ICH guidelines, the IRB/IEC, European regulation 536/2014 for clinical studies (if applicable), European Medical Device Regulation 2017/745 for clinical device research (if applicable), and all other applicable local regulations

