10.5. Appendix 5: Adverse Events of Special Interest (AESIs)

The following adverse events (AEs) for potential immune-mediated medical conditions as well as events associated with thrombosis and thrombocytopenia are AEs of special interest (AESIs) and include new onset of chronic illness (NOCIs). These events should be monitored for actively throughout the entire study period and reported to the Sponsor in an expedited manner as outlined in Section 10.3.

Gastrointestinal disorders:	Liver disorders:		
Celiac disease	Autoimmune cholangitis		
Crohn's disease	Autoimmune Hepatitis		
Ulcerative colitis	Primary biliary cirrhosis		
Ulcerative proctitis	Primary sclerosing cholangitis		
Metabolic diseases:			
Addison's disease	Diabetes mellitus type 1		
Autoimmune thyroiditis (including Hashimoto thyroiditis)	Grave's or Basedow's disease		
Coagulopathy:			
Acquired amegakaryocytic thrombocytopenia	Amegakaryocytic thrombocytopenia		
Axillary vein thrombosis	Cavernous sinus thrombosis		
Cerebral venous thrombosis	Deep vein thrombosis		
Disseminated intravascular coagulation	Embolism venous		
Hepatic vein thrombosis	Immune thrombocytopenia		
Intracranial venous sinus thrombosis	Mesenteric vein thrombosis		
Portal vein thrombosis	Pulmonary embolism		
Pulmonary thrombosis	Pulmonary venous thrombosis		
Severe fever with thrombocytopenia syndrome	Subclavian vein thrombosis		
Thrombocytopenia	Thrombocytopenia purpura		
Thrombotic thrombocytopenia purpura	• Thrombosis		
Transverse sinus thrombosis	Vena cava embolism		
Vena cava thrombosis	Venous thrombosis		
Musculoskeletal disorders:			
Antisynthetase syndrome	Polymyalgia rheumatic		
Dermatomyosotis	Polymyositis		
• Juvenile chronic arthritis (including Still's disease)	Psoriatic arthropathy		
Mixed connective tissue disorder	Relapsing polychondritis		
• Scleroderma, including diffuse systemic form and CREST Syndrome	Rheumatoid arthritis		
Systemic lupus erythematous	Systemic sclerosis		
• Spondyloarthritis, including ankylosing spondylitis, reactive arthritis (Reiter's Syndrome) and undifferentiated spondyloarthritis.			

Neu	Neuroinflammatory disorders:				
•	Acute disseminated encephalomyelitis, including site specific variants (e.g., non-infections encephalitis, encephalomyelitis, myeloradiculomyelitis)				
•	• Immune related peripheral neuropathies and plexopathies, including chronic inflammatory demyelinating polyneuropathy, multifocal motor neuropathy and polyneuropathies associated with monoclonal gammopathy				

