10.6 Appendix 7: Summary of Changes to Protocol

PROTOCOL VXA-NVV-105 HISTORY:			
Document	Date		
Protocol Amendment 1; Version 2.0	25 August 2021		
Original Protocol; Version 1.0	31 March 2021		

Overall Rationale for the Amendment:

Per a request received from the FDA, Vaxart has amended this clinical protocol to incorporate information on the risk of Thrombosis with Thrombocytopenia Syndrome (TTS) that has been observed with administration of two injected adenovirus-vectored COVID-19 vaccines being used under EUA. Enrollment under this protocol has completed, however subjects are currently in safety follow-up. All subjects will be reconsented with an updated informed consent form with updated risk information incorporating TTP at their next site visit. This requirement for updatd risk information has necessitated the modifications listed in the table below within protocol amendment 1 (Ver. 2.0). Additional minor changes incorporated into the amendment for added consistency/clarity are also summarized below.

Section No. & Title	Description of Change	Brief Rationale
Table 1.2: Schedule of Activities	Table 1 has been updated to include allocation of an aliquot of serum collected at baseline to be stored for testing (e.g. PF4 antibody ELISA) should an AESI related to blood clots be reported anytime during the study period.	Per the direction of the FDA, a blood sample should be collected at baseline and stored for analysis should a participant experience a clotting adverse event.
2.3 Benefit/ Risk Assessment	The risk section has been updated to include language describing the adverse events reported with two injected adenovirus- vectored vaccines (thromboembolism and/or thrombocytopenia), as well as with general information on how to monitor for and report the events should they occur in study participants.	Because Vaxart's VXA-G1.1-NN investigational vaccine utilizes an adenovirus vectored design, and per the director of the FDA, information on the risks of thromboembolism and /or thrombocytopenia have been added to Section 2.1 of the protocol.
Appendix 5: Adverse Events of Special Interest (AESIs)	The List of Adverse Events of Special Interest (AESIs) has been updated to include events to be monitored under the category of Coagulopathy	Per the guidance received from FDA, the list of AEs of special interest (AESIs) has been updated to require sites to monitor study participants for the occurrence of TTS events.

Protocol Clarifications

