Blood Sample (HBsAg, HCV, HIV)	Х									
Urine drug screen	Х									
Serum Pregnancy Test ^a	Х	Х		x1		X ²		x ³		
Physical examination	Х	Xb	xb	xb	Xb	xb	Xb	xb	Xb	Xb
Vital Signs	Х	Х	Х	Х	Х	Х	Х	Х	Х	Х
Safety laboratory tests	Х	Xc	Х	Х	Х	Х	Х	Х	Х	Х
Urinalysis	Х	Х	Х	Х	Х	Х	Х	Х	Х	Х
COVID vaccination status	Х									
Vaccination		Х		X ^{1, d,e}		X,2, d,e		x ^{3, d,e}		
Dispense Solicited Symptom Diary		x ^{1,2,3}		x ¹		X ²		x ³		
Review & Collect Solicited Symptom Diary			Х		x1		x ²		X ³	
Review prior & concomitant medication	Х	Х	Х	Х	Х	Х	Х	Х	Х	Х
Query for AEs, SAEs, AESIs andNOCIs		Х	Х	Х	X ^{1,f}	x ^{1,f}	x ^{2,f}	X ^{2,f}	X ^{3,f}	x ^{3,f}
Sample Collection Immunogenicity Assessments	·								-	•
Serum		x ^{1,2,3^g}		x ^{1,2,3}		x ^{1,2}		x ^{2,3}		x ³
Whole blood (Flow-Based)		x ^{1,2,3}	x ^{1,2,3}	x ¹	x ¹	x ²	x ²	x ³	x ³	
Whole blood (PBMC)		x ^{1,2,3}	x ^{1,2,3}	X ¹	X ¹	x ²	x ²	x ³	x ³	
Nasal Swab (Sam Device)		x ^{1,2,3}		x ^{1,2,3}		x ^{1,2}		x ^{2,3}		x ³
Saliva Sample		x ^{1,2,3}		x ^{1,2,3}		x ^{1,2}		x ^{2,3}		x ³

Vaxart Biosciences, Inc.; VXA-NVV-105

Version: Final v2.0, Date: 18-AUG-2021

¹ = Cohort 1; ² = Cohort 2; ³ = Cohort 3.

^a For women of childbearing potential. Test at Day 1 and at second dose (boost). Test at 2nd Study drug administration visit can be serum or urine test.

^b Targeted.

^c If screening lab tests are performed within 2 days prior to dosing, no need to repeat at Day 1.

^d Assess eligibility to receive second dose. Participants with acute illness or new medical condition may be re-assessed, and if the condition resolves, have a delayed 2nd dose within 1 week of scheduled visit.

^e If participants are not eligible to receive their 2nd dose, they immediately enter the follow-up period.

f AEs will only be collected for 4 weeks following each study drug administration.

^g An aliquot of serum collected at baseline will be stored for testing (e.g. Platelet Factor 4 [PF4] antibody ELISA) should an AESI related to blood clots be reported anytime during the study period.

Table 3 – Schedule	of Events	(Follow-up Period)
--------------------	-----------	--------------------

Follow-Up Period						
COHORT 1 COHORT 2 COHORT 3						
Study Day	Months 3, 4, 5, 6	Month 7 (Wk 28)/ EOS	Months 4, 5, 6, 7	Month 8 (Wk 32)/EOS	Months 5, 6, 7, 8	Month 9 (Wk 36)/EOS
Telephone Visit	Х		Х		Х	
Visit Window (days)	±7	±7	±7	±7	±7	±7
Query for SAEs, AESIs and NOCIs	Х	X	Х	Х	Х	Х
Sample Collection Immunogenicity Asses	ssments					
Serum		Х		Х		Х

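### Amendment 1 times the updated TTS risk information at the next site visit, which in follow-up is scheduled only at End of Study; the next monthly call would give it nominally 4 to 16 weeks sooner

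*Protocol*

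**What the plan says.** The rationale for Amendment 1 (Protocol Appendix 7, Summary of Changes) sets the timing: "All subjects will be reconsented with an updated informed consent form with updated risk information incorporating TTP at their next site visit". The sentence uses the abbreviation TTP, but its paragraph is about TTS and I read it so. It is a forward instruction, not a description of replaced text. The sentence before it gives the status of the trial: "Enrollment under this protocol has completed, however subjects are currently in safety follow-up".

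Five other places bear on the point.

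- **Follow-up contacts.** Protocol Section 4 says "participants will be contacted monthly by phone between site visits to monitor for safety as specified in the SoA". In the follow-up schedule (Protocol Section 1.2; SAP Section 3.3, Table 3) each cohort has four contacts marked "Telephone Visit", then one sampling visit, which for Cohort 1 is "Month 7 (Wk 28)/ EOS". The row "Query for SAEs, AESIs and NOCIs" is marked at every one of these contacts. Giving new risk information is not a listed activity at any of them.
- **Symptom instruction.** Protocol Section 2.3 separately wants participants told to seek care for a list of TTS symptoms. It names no date and no contact for this.
- **Surveillance.** Protocol Appendix 5, whose list of adverse events of special interest (AESIs) now includes clotting events, says "These events should be monitored for actively throughout the entire study period".
- **Re-consent rule.** Protocol Section 10.1.3 requires re-consent to the current form while the participant is in the study, with no earlier deadline.
- **Start of the clock.** Protocol Section 10.1.1 says "Any amendments to the protocol will require IRB/IEC approval before implementation of changes made to the study design". The approval date is not in the documents.

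**The concern.** The only written time for the updated risk information is a site visit, and the amendment describes a trial whose participants are in a phase run by telephone. Read with the schedule, the instruction places the information at the last contact of the study for anyone already in follow-up. A symptom warning first given then cannot help a participant recognise an event during follow-up. A participant who answers calls but is lost before End of Study would have no written occasion to receive it.

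What is at stake is participant safety information. The sponsor asks for active monitoring over the whole study period, and between monthly calls that depends partly on participants knowing what to report.

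**Working it through.** **Inputs.** Calls are at Months 3 to 6 (Cohort 1), 4 to 7 (Cohort 2) and 5 to 8 (Cohort 3). End of Study is Month 7 (Week 28), Month 8 (Week 32) and Month 9 (Week 36). Every follow-up contact has a window of ±7 days. The Active Period ends at Week 8, 12 and 16. All are from Protocol Sections 1.2 and 4 and SAP Section 3.3.

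**Reproducing the plan's weeks.** With 4-week months, 7 × 4 = 28, 8 × 4 = 32 and 9 × 4 = 36, as printed. Calendar months (365.25 / 84 = 4.348 weeks) would give 30.4, 34.8 and 39.1, which do not match. One study month is therefore 4 weeks.

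**Nominal gain.** Gain = End of Study week − week of the next scheduled call.

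| Cohort | Call weeks | End of Study week | Gain at call 1, 2, 3, 4 (weeks) |
|---|---|---|---|
| 1 | 12, 16, 20, 24 | 28 | 16, 12, 8, 4 |
| 2 | 16, 20, 24, 28 | 32 | 16, 12, 8, 4 |
| 3 | 20, 24, 28, 32 | 36 | 16, 12, 8, 4 |

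After the fourth call the next contact is End of Study itself, so the gain is 0.

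**Visit windows.** The shortest gain is (End of Study − 1) − (call + 1), which is nominal − 2 weeks. The longest is (End of Study + 1) − (call − 1), which is nominal + 2 weeks. The ranges are 14–18, 10–14, 6–10 and 2–6 weeks, or 2 to 18 overall.

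**Sensitivity.** If the calls were made on calendar months, the gains would run from 1 × 4.348 = 4.3 to 4 × 4.348 = 17.4 weeks.

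**Longest wait as written.** A participant who has just finished the Active Period when the amendment is approved waits 28 − 8 = 32 − 12 = 36 − 16 = 20 weeks for the next scheduled site visit.

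**Could everyone have been past the fourth call?** This is hypothetical, because no dosing date is given. Suppose nobody was dosed before the date of the original protocol, 31 March 2021. From then to the amendment date, 25 August 2021, is 147 days, or 147 / 7 = 21 weeks. The fourth calls fall at Weeks 24, 28 and 32, so on the amendment date every participant would still have had a call ahead. A gain of zero then needs approval more than 3, 7 or 11 weeks later, for the earliest possible participant in Cohorts 1, 2 and 3 respectively. This describes an assumed participant, not this trial, and the conclusion does not rest on it.

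**The case against.** The case on the other side is substantial, and most of it stands.

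- **The instruction times re-consent, not first disclosure.** A reader might infer that the plan withholds the TTS warning until the last visit. The documents do not support that. Nothing bars a site from informing participants earlier, and the Section 2.3 instruction is not tied to the form or to a site visit. What is left is that no earlier time is written.
- **End of Study is only the next scheduled site visit.** Protocol Section 8 has participants with serious or severe events, or any event of concern, contact the site and be booked for a visit. Such a visit could come sooner.
- **Surveillance does not depend on re-consent.** The monthly calls ask about AESIs in any case.
- **Most of the risk period has passed.** Section 2.3 puts typical onset within 4 weeks of vaccination, most commonly 1 to 2 weeks. Follow-up starts 4 weeks after the last dose, and no further dose is given. Participants still in the Active Period have earlier site visits, so the instruction works for them. This stands and keeps the benefit small. It does not remove it, because Appendix 5 still asks for active monitoring to the end of the study.
- **Call scripts, participant letters and the consent form are not in the documents.** They may already give the warning by phone. A reader might also infer that participants were in fact warned late; that cannot be determined.

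None of this supplies a written time earlier than the next site visit.

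**Conclusion.** The point holds as a low-severity, inexpensive improvement. For a participant in follow-up at approval, the written time for the updated TTS risk information is, by the schedule, End of Study, and the symptom instruction has no written time at all. Using the next call brings the information forward by nominally 16, 12, 8 or 4 weeks, the same in all cohorts, and by 0 once the fourth call has passed.

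This rests on 4-week study months, contacts at their scheduled times apart from the windows, and no unscheduled visit in between. The number of participants affected is unknown and at most 30.

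A reader might infer a breach of the consent rules. There is none: re-consent at End of Study still falls within participation, which is all that Section 10.1.3 asks. No endpoint or analysis is affected.

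**What to change.** State in the amendment that, once it is approved, the updated risk information and the Section 2.3 symptom list are given and documented at the next scheduled contact of any kind, including the monthly call. The revised form is then signed at the next site visit.

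The cost is a few minutes in calls that already take place, a line of documentation, and IRB review of the wording. No remote-consent procedure is needed: the form, which the person obtaining consent must also sign (Section 10.1.3), can still be signed on site. If scripts or letters already give the warning by phone, writing that timing into the amendment closes the point.

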MSD NOCI	New erest of elemenic illeges
	New onset of chronic liness
	Peripheral plood mononuclear cells
	Principal investigator
	Pet protocol
	Partial thromhonloctin time
	Paruar uniompopiasun ume
SAE	Serious adverse event

Abbreviation	Explanation
SAP	Statistical analysis plan
SD	Standard deviation
SI	Standard international
SOC	System organ class
SoE	Schedule of Events
TLF	Tables, listings and figures
ULN	Upper limit of normal
VP1	Vaccine protein 1
WBC	White blood cell

1.0 Introduction

The purpose of this Statistical Analysis Plan (SAP) is to provide detailed descriptions of the statistical methods, data derivations, and data displays for the study protocol VXA-NVV-105 Original "A Phase 1b, open-label, boost-optimization study of an adenoviral-vector based oral norovirus vaccine (VXA-G1.1-NN) expressing GI.1 VP1 administered orally to healthy adult volunteers" dated 31-MAR-2021 for final analysis. The table of contents and templates for the table, listing and figures (TLFs) will be produced in a separate document.

Any deviations from this SAP will be described and justified in the Clinical Study Report (CSR).

The preparation of this SAP has been based on International Council for Harmonisation (ICH) E9 and Good Clinical Practice (GCP) guidelines.

All data analyses and generation of TLFs will be performed using SAS 9.4[®] (or higher).

2.0 Study Objectives

2.1 Primary objective

To evaluate the immunogenicity of VXA-G1.1-NN with repeat-dose administration at Day 1 and varying boost schedules (Week 4, 8 or 12 post initial dose) in healthy adults aged 18-55, inclusive.

2.2 Secondary objective

To assess the safety and tolerability of VXA-G1.1-NN with repeat-dose administration at varying boost schedules (Week 4, 8 or 12) in healthy adults aged 18-55, inclusive.

2.3 Exploratory objectives

- To assess additional safety parameters
- To assess long-term safety of VXA-G1.1-NN through 6 months after last vaccination
- To assess additional immunogenicity parameters of VXA-G1.1-NN

2.4 Safety objectives

Safety objectives are included as part of the secondary and exploratory objectives.

3.0 Study Design

3.1 General study design

This is a Phase 1b, open-label, boost-optimization study to evaluate the immunogenicity, safety and tolerability of VXA-G1.1-NN with repeat-dose administration at Day 1 and varying boost schedules in healthy

adult subjects aged 18 - 55. Thirty subjects will be enrolled to one of the three treatment cohorts (10 subjects in each cohort) with varying boosting vaccination schedules at Week 4, 8 or 12, respectively, post the initial vaccination on Day 1 such that each subject will receive two doses of 1×10^{10} IU ± 0.5 log in total. See study protocol Section 5 for inclusion and exclusion criteria.

On Day 1, participants will be enrolled sequentially in order of eligibility. Participants may be assigned to cohorts based on their availability for the second dose (boost). Cohorts 3 and 2 will be enrolled prior to Cohort 1 to optimize the overall study timeline.

Group	Study Drug	Dose (IU ±0.5 log)	Doses	Dosing Schedule	Subjects
Cohort 1	VXA-G1.1-NN	1x10 ¹⁰	2	Day 1 & Week 4	10
Cohort 2	VXA-G1.1-NN	1x10 ¹⁰	2	Day 1 & Week 8	10
Cohort 3	VXA-G1.1-NN	1x10 ¹⁰	2	Day 1 & Week 12	10
				Total	30

Table 1: Treatment Arm, Doses and Sample Sizes

The study will include a Screening period, Study Period 1, Study Period 2, and a Follow-up Period:

- Screening Period (Day -45 to -1)
- Study Period 1 (Day 1 to 4 weeks post initial vaccination)
- Study Period 2 (4 weeks from the second vaccination: Week 4 to Week 8 for Cohort 1; Week 8 to Week 12 for Cohort 2; Week 12 to Week 16 for Cohort 3)
- Follow-up Period (6 months post the second vaccination for each cohort: Month 7 for Cohort 1, Month 8 for Cohort 2 and Month 9 for Cohort 3)

